7.9.3. HRU in the 205MS302-303 ITT Population

For the 205MS302-303 ITT population, the total number of unscheduled site visits per collection time will be summarized separately for MS-related and non-MS related visits. The annualized rate of unscheduled site visits will be calculated as the total number of unscheduled visits collected on Patient Health Care Treatment CRF page, divided by the total number of years.

7.10. Health Related Productivity Questionnaire (HRPQ)

7.10.1. HRPQ in the 205MS301-303 ITT Population

For the 205MS301-303 ITT population, responses to the HRPQ will be summarized by 205MS301 treatment group in the 205MS303 Treatment Period.

7.10.2. HRPQ in the 205MS203-303 ITT Population

For the 205MS203-303 ITT population, responses to the HRPQ will be summarized in the 205MS303 Treatment Period.

7.10.3. HRPQ in the 205MS302-303 ITT Population

For the 205MS302-303 ITT population, responses to the HRPQ will be summarized in the 205MS303 Treatment Period.

7.11. Symbol Digit Modalities Test (SDMT)

For the 205MS301-303 ITT population, SDMT actual value and change from 205MS301 baseline will be summarized by 205MS301 treatment group in the Combined Study Period (by study visit in 205MS301 and 205MS303 studies). Additionally, proportion of patients with ≥ 3 points or ≥ 4 points increase from 205MS301 baseline, and proportion of patients with ≥ 3 points or ≥ 4 points decrease from 205MS301 baseline will be summarized by 205MS301 treatment group in the Combined Study Period (see also, Benedict et. al 2017). Similar analyses will be done for the 205MS303 treatment period with changes from 205MS303 baseline. Note that in the 205MS303 study, SDMT is only collected for subjects in 205MS301-303 ITT population starting from week 144 in the study.

SDMT is not collected for patients enrolled from the 205MS203 or 205MS302 study to the 205MS303 study.

7.12. 3 Second Paced Auditory Serial Addition Test (PASAT3)

For the 205MS301-303 ITT population, PASAT3 actual value and change from 205MS301 baseline will be summarized by 205MS301 treatment group in the Combined Study Period (by study visit in 205MS301 and 205MS303 studies). Similar analyses will be done for the 205MS303 treatment period with changes from 205MS303 baseline.

Note that PASAT3 is not collected for patients enrolled from the 205MS203 or 205MS302 study to the 205MS303 study.

7.13. Proportion of subjects who are free from disease activity

Subjects were considered free of disease activity if they were without clinical or radiological activity. Clinical activity included an assessment of relapses and of disease progression, and radiological activity included an assessment of Gd+ lesions and new or enlarging T2 lesions.

For the 205MS301-303 ITT population, proportion of subjects who are free from disease activity in the 205MS303 treatment period will be summarized by 205MS301 treatment group.

8. Safety Data

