The design of Study 205MS303 is provided in [Figure 1](#). Approximately 1500 subjects will enroll in this study. This includes approximately 1200 subjects who completed Study 205MS301. Additionally, approximately 300 subjects from the other DAC HYP extension studies (205MS203 [SELECTED] and 203MS302 [OBSERVE]) will be eligible to enter Study 205MS303 at Week 144 of Study 205MS303 (Study 205MS301, Study 205MS203, and Study 205MS302 have been referred to as parent studies in the protocol).

All subjects will receive the same dose of DAC HYP as received in the parent studies; i.e., 150 mg by a subcutaneous (SC) injection every 4 weeks. The duration of DAC HYP treatment is up to approximately 5 years, or until availability of commercial product (whichever is sooner). Note that per sponsor discretion, the study was closed early and dosing was terminated by March 30th, 2018.

Figure 1: Study Design for 205MS303 study

¹Subjects who do not enter Study 205MS303 will complete post-dosing safety follow-up visits per the parent study protocol.

	
Protocol 205MS303 Statistical Analysis Plan for the Interim Analysis
	
Final Version 3.0

--	---	--

3. Schedule of Events

Table 1: Schedule of Activities: Baseline Through Week 84 for Subjects Enrolling From Study 205MS301 Into Study 205MS303

Note: If study treatment is temporarily suspended or withheld for abnormal liver function tests (LFTs), LFTs must be re-evaluated as specified in Protocol Section 11.7.2. A window of ± 4 days applies to all the visits.

Tests and Assessments ^{1,2}	Week 0/ Day 1 Baseline Visit ³	Week 4 ± 4 days	Week 8 ± 4 days	Week 12 ± 4 days	Week 24 ± 4 days	Week 36 ± 4 days	Week 48 ± 4 days Start Year 2	Week 60 ± 4 days	Week 72 ± 4 days	Week 84 ± 4 days
Informed Consent	X									
Confirm Eligibility	X									
Medical History Update, including Tobacco Use	X									
Physical Exam	X			X	X		X		X	
Vital Signs (Pre-dose)	X			X	X		X		X	
Weight	X									
Hematology	X			X	X		X		X	
Blood Chemistry (except LFTs)	X			X	X		X		X	
Liver Function Tests ⁴		Liver function testing to be performed within the previous 32 days (see Protocol Section 14.4.3)								
Liver Function Tests at Central Laboratory ^{4, 5}	X	X	X	X	X	X	X	X	X	X
Thyroid Function Panel	X									
DAC HYP Concentration Assessment	X			X	X		X			
Serum Biomarker Sample	X			X	X		X			
Urine Biomarker Sample	X						X			
RNA Assessment	X			X	X		X			
DNA Collection (Optional) ⁷										

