Liver Function Tests at Central Laboratory ^{2 3}	X	X	X	X	X	X	X	X
DAC HYP Concentration Assessment				X				X
Anti-Drug Antibody Sample				X				X

Tests and Assessments	Week 156 ±4 days	Week 168 ±4 days	Week 180 ±4 days	Week 192 ±4 days Start Year 5	Week 204 ±4 days	Week 216 ±4 days	Week 228 ±4 days	Week 240 ±4 days End of Treatment/ Early Termination Visit ¹ 4 Weeks After Last Dose
Urine Pregnancy Test ⁵		X		X		X		X
EQ-5D and EQ-VAS				X				X
HRU				X				X
HRPQ		X		X		X		X
MRI ⁶				X				X ⁷
EDSS ⁸		X		X		X		X
SDMT ⁹		X		X		X		X
PASAT 3 ⁹		X		X		X		X
DAC HYP Administration/Dispensation ^{10 11}	X	X	X	X	X	X	X	
Dosing Diary	Subject to record observations during home dosing only							
Physician Global Assessment Scale	Performed only in subjects with cutaneous AEs (see Protocol Section 11.7.3)							
Concomitant Therapy and AEs	Monitor and record throughout the study.							
Protocol Compliance and DAC HYP Accountability	Monitor and record throughout the study.							

- ¹ For subjects who prematurely discontinue dosing, the End of Treatment (Early Termination) Visit should be performed 28 ± 4 days following the subject's last dose of study treatment.
- ² ALT/SGPT, AST/SGOT, alkaline phosphatase, total bilirubin, and GGT only.
- ³ If local LFTs have been used to determine whether dosing should continue or be suspended at the time of a scheduled clinic visit, LFTs must also be performed at the central laboratory at the time of the scheduled clinic visit (Note: Scheduled clinic visits occur every 12 weeks)
- ⁵ Pregnancy test results must be negative prior to dosing.
- ⁶ MRI scan can be performed up to 4 days prior to the visit.
- ⁷ MRI assessment is optional for the Early Termination visit. Under protocol version 4, MRI assessments were added at Weeks 192 and 240 to better assess the efficacy of daclizumab on MRI outcomes over a longer period of time as compared to the previous version of the protocol, in which the last MRI assessment was at Week 144.
- ⁸ When possible, subjects should be evaluated by the same neurologist assigned to them in the parent studies.
- ⁹ Performed only for subjects originally enrolled from Study 205MS301 under protocol version 3 and thereafter.
- ¹⁰ Before a monthly dose of DAC HYP is given, LFT results from a prior test performed within the previous 32 days must be reviewed by the *Study Neurologist* or their backup.
- ¹¹ A window of ± 4 days applies to DAC HYP dose even if it is done at home.

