5.3. Key Dates Time Period Definitions

The following time periods will be defined for efficacy and safety analyses:

205MS301 Treatment Period

The 205MS301 Treatment Period is the time period as defined in the 205MS301 statistical analysis plan and includes data collected from the first dosing date to the end of treatment period visit in the 205MS301 study. For subjects who completed study treatment this is the date of the last scheduled treatment period visit in that study.

205MS303 Treatment Period refers to the time between the first dose date in 205MS303 and the date of the last available measurement prior to 180 days after the last dose date in 205MS303. This is the time period for most of the efficacy analyses and for all the safety analyses for all the populations.

Combined Study Period

For the 205MS301-303 ITT population, the Combined Study Period is the combined period of the 205MS301 and 205MS303 studies, that is the time between the first dose date in 205MS301 and the date of the last available measurement prior to 180 days after last dose date in 205MS303.

Note that for the 205MS203-303 ITT population and the 205MS302-303 ITT population, the combined study period is not necessary due to the limited number of patients in each population.

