SDMT: actual score and change from baseline; proportion of subjects with a ≥ 3 or ≥ 4 decline from baseline; proportion of subjects with a ≥ 3 or ≥ 4 increase from baseline.	205MS301-303 ITT population	Combined Study Period	205MS301 Baseline	Descriptive statistics by previous treatment group in 205MS301 and by study visit in 205MS301 and 205MS303.
		205MS303 Treatment Period	205MS303 Baseline	Descriptive statistics by previous treatment group in 205MS301 and by study visit in 205MS303.
MSIS-29 physical score and MSIS-29 psychological score: actual score and change from baseline; proportion of subjects with a ≥ 7.5 worsening from baseline in MSIS-29 physical score.	205MS301-303 ITT population	205MS303 Treatment Period	205MS303 Baseline	Descriptive statistics by previous treatment group in 205MS301 and by study visit in 205MS303.
Proportion of subjects who are free from disease activity	205MS301-303 ITT population	205MS303 Treatment Period	205MS303 Baseline	Descriptive statistics by previous treatment group in 205MS301
HRU: MS-related and non-MS related visits	205MS301-303 ITT population	205MS301 Treatment Period		Descriptive statistics for the number of unscheduled site visits by previous treatment group in 205MS301 and by visit in 205MS301 study.
		205MS303 Treatment Period		Descriptive statistics for the number of unscheduled site visits by previous treatment group in 205MS301 and by visit in 205MS303 study.
HRPQ	205MS301-303 ITT population	205MS303 Treatment Period		Descriptive statistics by previous treatment group in 205MS301 and by study visit in 205MS303 study.

Table 9: Summary of efficacy analyzes for the 205MS203-303 ITT population

Endpoint	Study/Treatment Period	Baseline	Statistical Methods
Annualized relapse rate	205MS303 Treatment Period	205MS303 Baseline	Unadjusted and adjusted ARR for all subjects combined. Adjusted ARR will be estimated from the negative binomial/Poisson model, adjusting for baseline relapse rate at the 205MS303 Baseline
Annualized relapse rate by 48-week time interval	205MS303 Treatment Period	205MS303 Baseline	Unadjusted and adjusted ARR for all subjects combined. Adjusted ARR will be estimated from the Poisson model, adjusting for baseline relapse rate at the 205MS303 Baseline.
Proportion of subjects who relapsed at selected time points	205MS303 Treatment Period	205MS303 Baseline	Kaplan-Meier curve of time to first relapse will be used to estimate the proportion at selected time points for all subjects combined

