7.3. Proportion of Subjects who Relapsed

7.3.1. Proportion of Subjects with Relapse in the 205MS301-303 ITT Population

The proportion of subjects who relapsed will be summarized using the following study population and study periods

- 205MS301-303 ITT population in the combined study period
- 205MS301-303 ITT population in the 205MS303 Treatment period

Relapse will be defined using the same definition that was used for the annualized relapse rate endpoint. The proportion of subjects who relapsed at selected time points, by treatment group of the 205MS301 study, will be estimated.

Kaplan-Meier curve of time to the first relapse during the study period (i.e., the Kaplan-Meier product-limit estimator) will be used to estimate the proportion of subjects who relapsed. If there are no early withdrawals, the Kaplan-Meier estimate of the proportion of subjects relapsed is same as the observed proportion of subjects relapsed. If there are early withdrawals, the Kaplan-Meier estimate has the advantage of taking into account the length of follow-up for the early withdrawals, without having any assumptions about whether those subjects relapsed or not.

Subjects without a confirmed relapse will be censored at either early withdrawal or the end of the corresponding study period. If a subject took an alternative MS medication before the first relapse, the subject will be censored at the time of the alternative MS medication. Kaplan-Meier plots of the

	Protocol 205MS303 Statistical Analysis Plan	Final Version 1.0
---	--	--------------------------

time to first relapse will also be presented and used to estimate the median time (and/or the 25th percentile) by the previous treatment group of the 205MS301 study.

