The total number of T2 lesions at 205MS303 baseline will be calculated by summing the 205MS301 baseline number of T2 lesions and the number of new or newly enlarging lesions since the previous visit at 205MS301 Week 24, 205MS301 Week 96, 205MS301 Week 144 (if available) and 205MS303 Baseline (if available). The same algorithm will be applied to the total number of T1 lesions and the total volume of T1 lesions at 205MS303 baseline.

Data obtained after alternative MS medication will be set to missing. Missing data will not be imputed.

The total number of new or newly enlarging T2 hyperintense lesions

The number of new or newly-enlarging T2 hyperintense lesions relative to the 205MS301 baseline will be analyzed for Week 24 and Week 96 of the 205MS301 study. The number of new or newly-enlarging T2 hyperintense lesions relative to the 205MS303 baseline will be analyzed for Weeks 48, 96, 144, 192, and 240 (if available) of the 205MS303 study.

A negative binomial regression model will be used to analyze the observed new or newly enlarging T2 lesions. The model for the analysis relative to the 205MS301 baseline will be adjusted for the following characteristics at the 205MS301 baseline: volume of T2 hyperintense lesions, history of prior IFN β use and baseline age (age \leq 35 versus age $>$ 35). The model for the analysis relative to

	Protocol 205MS303 Statistical Analysis Plan	Final Version 1.0
---	--	--------------------------

the 205MS303 baseline will be adjusted for the following characteristics: the volume of T2 hyperintense lesions at the 205MS303 baseline, history of prior IFN β use at the 205MS301 baseline, and baseline age (age \leq 35 versus age $>$ 35) at the 205MS303 baseline.

The total number of new T1 hypointense lesions

The total number of new T1 hyperintense lesions relative to the 205MS301 baseline and the 205MS303 baseline will be analyzed using the same methodology as for the analysis new or newly-enlarging T2 hyperintense lesions. The estimated number of lesions will be evaluated using negative binomial regression, adjusted for the history of prior IFN β use at the 205MS301 baseline, age (age \leq 35 versus age $>$ 35) at the corresponding baseline, and volume of T1 hypointense lesions at the corresponding baseline.

Number of Gd-Enhancing Lesions

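### Freedom from disease activity is one crude proportion over unequal follow-up, so it varies with drop-out and is not freedom at any given week

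*SAP*

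**What the plan says.** - **Definition (Section 7.13).** "Subjects were considered free of disease activity if they were without clinical or radiological activity". Clinical activity covers relapse and progression. Radiological activity covers Gd-enhancing lesions and new or enlarging T2 lesions.
- **Estimator.** Section 7.13 says that the "proportion of subjects who are free from disease activity in the 205MS303 treatment period will be summarized by 205MS301 treatment group". Table 8 names the 205MS301-303 ITT population and the method "Descriptive statistics by previous treatment group in 205MS301". Neither place gives a time point, a minimum follow-up, a required MRI or a censoring rule.
- **Period.** Under Section 5.3 the 205MS303 Treatment Period runs from first dose to the "date of the last available measurement prior to 180 days after the last dose date in 205MS303". Section 2 says "The duration of DAC HYP treatment is up to approximately 5 years, or until availability of commercial product (whichever is sooner"), and that dosing stopped by 30 March 2018 because the sponsor closed the study early.
- **MRI.** Tables 1, 2 and 4 schedule post-baseline scans at Weeks 48, 96, 144, 192 and 240. Table 4, footnote 7: "MRI assessment is optional for the Early Termination visit". Section 7.6.1: "Data obtained after alternative MS medication will be set to missing. Missing data will not be imputed".
- **Components analysed alone.** Section 7.3.1 uses Kaplan-Meier for relapse because "the Kaplan-Meier estimate has the advantage of taking into account the length of follow-up for the early withdrawals". Section 7.4.1 uses Kaplan-Meier with explicit censoring for confirmed progression.

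**The concern.** A subject followed for months has had less opportunity to show activity than one followed for years, yet both enter the same proportion with equal weight. Radiological activity can be recorded only at a scan. A subject who stops before Week 48 without relapse or progression may never have a post-baseline scan.

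The figure therefore reflects how long subjects stayed as well as how active their disease was. It does not estimate freedom at Week 48, Week 144 or any other week. Because it is reported by 205MS301 treatment group, unequal drop-out between the groups could appear as a difference in disease control, or hide one. The SAP meets this problem with Kaplan-Meier for relapse and progression, but not for the composite that contains them.

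**Working it through.** The SAP gives no figure for this endpoint, so there is none to reproduce. The calculation shows how the planned proportion behaves under stated assumptions.

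**Inputs from the SAP.** Scans every 48 weeks, a horizon of 240 weeks, and about 1200 subjects from 205MS301 (Section 2).

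**Assumptions, not in the SAP.** One-year freedom from activity is 65% with a constant hazard. Of the activity hazard, 35% is clinical and seen at once; the rest is MRI activity, seen at the next scan. Drop-out is constant at 10% or 20% a year and independent of activity. There is no scan at early termination. One year is 52.18 weeks.

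**Weekly hazards**
- Total activity: h = −ln(0.65)/52.18 = 0.00826. Clinical: c = 0.35h = 0.00289. MRI: m = 0.65h = 0.00537.
- Drop-out: d = −ln(0.90)/52.18 = 0.00202, or −ln(0.80)/52.18 = 0.00428.

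**True freedom.** exp(−144h) = 30% at Week 144; exp(−240h) = 13.8% at Week 240.

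**Proportion with no observed activity.** For subjects who leave between scan k and scan k+1 (k = 0 to 4), with a = d + c:

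P_k = exp(−48km) × (d/a) × [exp(−48ka) − exp(−48(k+1)a)]

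Subjects who reach Week 240 free of activity contribute F = exp(−240(d + h)).

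| | 10% a year | 20% a year |
|---|---|---|
| P_0 (no scan, no clinical activity) | 0.0864 | 0.1737 |
| P_0 + … + P_4 | 0.2030 | 0.3653 |
| F | 0.0849 | 0.0494 |
| A. Missing MRI counts as no activity: ΣP_k + F | 28.8% | 41.5% |
| B. Exclude the P_0 subjects: (A − P_0)/(1 − P_0) | 22.1% | 29.2% |
| C. Incomplete follow-up counts as failure: F | 8.5% | 4.9% |
| True Week 240 freedom | 13.8% | 13.8% |

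At 10% drop-out, P_0 is about 0.0864 × 1200 = 104 subjects. Two groups with identical disease but drop-out of 10% and 20% would differ by about 13 points under A and 7 under B. Under C they would differ by about 4 points the other way.

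**Sensitivity.** With one-year freedom of 80% (true Week 240 freedom 35.8%), A gives 48.7% and 59.2%, and B gives 43.7% and 50.3%. Varying the clinical share from 20% to 50% moves A and B by about 1 point or less.

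**Shorter horizon.** In a simulation to Week 144 with true freedom of 40% and 10% annual drop-out, A gave 48.3%, B 43.3%, C 29.7% and Kaplan-Meier 39.8%.

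**The proposed estimator.** Kaplan-Meier with events and censoring both cut at the last MRI was simulated with 400,000 subjects under the 65% assumption.

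| Week | True | KM, 10% drop-out | KM, 20% drop-out |
|---|---|---|---|
| 48 | 0.673 | 0.674 | 0.675 |
| 96 | 0.453 | 0.453 | 0.454 |
| 144 | 0.305 | 0.305 | 0.306 |
| 192 | 0.205 | 0.205 | 0.206 |

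If clinical events after the last MRI are counted while event-free subjects are censored at that MRI, the Week 144 estimate falls to 0.300 and 0.291. The two cuts must coincide.

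**The case against.** A reader might infer that the SAP counts an early leaver without an MRI as a success, and hence that drop-out inflates the result and flatters the group that loses more subjects. The text does not say so. Section 7.13 refers to an assessment of lesions, and Sections 5.4 and 7.6.1 rule out imputing missing data. Excluding unscanned subjects is therefore a fair reading, and a failure rule would turn the bias downward. A completers-only rule would be unbiased under independent drop-out, but it needs a fixed time point, which the SAP does not give.

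The assumed rates have no source in the SAP, and nothing there suggests that drop-out differs between the groups, all of whom receive DAC HYP in 205MS303. The endpoint is secondary and descriptive, the primary endpoints are adverse events, and no sample size rests on it. The components are also reported separately with defined timing.

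These points stand. They limit the size and certainty of the concern but do not remove it. Excluding subjects with neither a scan nor clinical activity still leaves an upward bias, because follow-up among the rest remains unequal. The spread between permissible rules, from 8.5% to 28.8% for one truth at 10% drop-out, is itself a reason to fix the estimator.

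**Conclusion.** The point holds in conditional form. As written, Section 7.13 and Table 8 yield one proportion over subject-specific follow-up, with no horizon, evaluable set or censoring. On the plain reading (ITT denominator, absence of activity), subjects who leave before the Week 48 MRI without clinical activity can count as free. The SAP does not state this, so upward inflation cannot be asserted as a certainty.

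With one-year freedom of 65% and true Week 240 freedom of 14%, the proportion is about 29% and 41% at 10% and 20% annual drop-out if a missing MRI counts as no activity. It is about 22% and 29% if subjects with neither a scan nor clinical activity are excluded. Counting incomplete follow-up as failure gives about 8% and 5%. These figures rest on constant hazards, drop-out independent of activity, and scans at all five weeks. Drop-out related to disease activity was not examined and could change both size and direction. The change should be made, though no primary conclusion depends on it.

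**What to change.** Replace the proportion in Section 7.13 and Table 8 with a Kaplan-Meier estimate of time to first disease activity, by 205MS301 treatment group, at Weeks 48, 96, 144 and 192. This matches Sections 7.3 and 7.4.

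- **Event:** the earliest of relapse, onset of confirmed progression, or an MRI with Gd-enhancing or new or newly enlarging T2 lesions.
- **Cut-off:** the last MRI before withdrawal, end of period or start of alternative MS medication. Count events only up to that MRI and censor event-free subjects there. A subject with no post-baseline MRI is then censored at baseline.

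Do not substitute the proportion among subjects who had activity by a given week or have complete data to it. That rule keeps early leavers with activity and drops those without, so drop-out biases it downward. In the Week 144 simulation with true freedom of 40%, it gave 36.5% at 10% annual drop-out.

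**Cost:** SAP wording and one reprogrammed table. Some clinical events after the last MRI go unused, and the reported proportion will probably be lower. Kaplan-Meier still assumes that leaving is unrelated to disease activity, as it does in Sections 7.3 and 7.4.
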